6.2 Consent

The Chief Investigator (PI) retains overall responsibility for the conduct of research which includes the taking of informed consent of participants at their site. The PI will ensure that any person delegated responsibility to participate in the informed consent process is duly authorised, trained and competent to participate according to the ethically approved protocol, principles of Good Clinical Practice (GCP) and Declaration of Helsinki.

Informed consent will be obtained prior to the participant undergoing procedures that are specifically for the purposes of the trial and are out-with standard routine care at the participating site.

The right of a participant to refuse participation without giving reasons will be respected.

The participant will remain free to withdraw at any time from the trial without giving reasons and without prejudicing his/her further treatment and will be provided with a contact point where he/she may obtain further information about the trial. Data and samples collected up to the point of withdrawal will only be used after withdrawal if the participant has consented for this. Any intention to utilise such data is outlined in the consent literature. Where a participant is required to re-consent or new information is required to be provided to a participant, the PI will ensure this is done in a timely manner.

The PI takes responsibility for ensuring that all vulnerable participants are protected and participate voluntarily in an environment free from coercion or undue influence.

The potential participant will discuss with an individual knowledgeable about the research about the nature and objectives of the trial and possible risks associated with their participation. The potential participant will have the opportunity to ask questions.

The written material (information leaflet and consent document) is approved by the REC and is in compliance with GCP, local regulatory requirements and legal requirements

All participants will be capable of giving consent for themselves:

- understand the purpose and nature of the research
- understand what the research involves, its benefits (or lack of benefits), risks and burdens
- understand the alternatives to taking part
- be able to retain the information long enough to make an effective decision.
- be able to make a free choice
- be capable of making this particular decision at the time it needs to be made

6.2.1 Additional consent provisions for collection and use of participant data and biological specimens in ancillary studies, if applicable: N/A

6.3 The randomisation scheme: N/A

6.3.1 Method of implementing the randomisation/allocation sequence: N/A

6.4 Blinding: N/A

6.5 Emergency Unblinding: N/A

6.6 Baseline data

The baseline data consist of: MADRS, tDCS AEQ, Acceptability questionnaire, PHQ-9, HAMA, YMRS, SDS, Q-LES-Q, EEG, AVLT, SDMT (Appendix 2).

6.7 Trial assessments

Trial assessments are described in Appendix 2.

6.8 Long term follow-up assessments

Long term follow-up assessments will be acquired at 3 months following the final treatment visit (Appendix 2).

Participants who do not respond to repeated attempts at contact will be identified as 'lost to follow-up'.

6.9 Qualitative assessments

At the final tDCS session, participants will complete the acceptability questionnaire and provide feedback on their experience of the study.

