6.10 Withdrawal criteria

Participants will be withdrawn from the trial if they do not comply with the intervention, namely if they are unable to have a minimum of 50% of the tDCS session (10 out of 21 sessions), or if they develop serious adverse effects from any part of the study. Recording of the reasons for withdrawal will be made. Should a participant lose capacity to consent during the study then they would be withdrawn from the study, and that their identifiable data already collected with consent would be retained for use, and that no further data collection would take place. Their GP will be informed about their withdrawal, and there will have a telephone follow up at 1 month following their withdrawal.

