9.3.2 Primary outcome analysis

The primary outcome analysis clinical response which will be measured by the number of enrolled participants who show a clinical response at the end of treatment (MADRS score improvement of $\geq 50\%$ following the course of tDCS treatment), divided by the total number of enrolled participants, expressed as a percentage.

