9.3.3 Secondary outcome analysis

The secondary outcome analyses are; participant retention, which will be measured by the number of enrolled participants who do not drop out before the 6 week course of tDCS, divided by the total number of enrolled participants, expressed as a percentage; Acceptability, which will be measured by the percentage of participants rating the intervention as acceptable at the end of the 6 week course of tDCS. The acceptability scale consists of the question 'How acceptable did you find the tDCS

sessions?' with responses ranging from 'Very unacceptable' to 'Very acceptable' on a 7-point anchored Likert scale with the acceptable ratings being from rating 5-7, and safety outcomes, which will be measured by calculating the number of severe, moderate and mild adverse events and their relation to the intervention.

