11 SCHEDULE OF EVENTS

Study Procedure	Screening	Treatment Period																				Follow up	
		V0	V1	V2	V3	V4	V5	V6	V7	V8	V9	V10	V11	V12	V13	V14	V15	V16	V17	V18	V19	V20	
Visit	V0	C/H	C/H	C/H	C/H	C/H	C/H	C/H	C/H	C/H	C/H	C/H	C/H	C/H	C/H	C/H	C/H	C/H	C/H	C/H	C/H	C/H/T	
Location		C/H	C/H	C/H	C/H	C/H	C/H	C/H	C/H	C/H	C/H	C/H	C/H	C/H	C/H	C/H	C/H	C/H	C/H	C/H	C/H	C/H	
Week of Treatment	Wk -4 to 0	Wk1	Wk1	Wk1	Wk1	Wk1	Wk2	Wk2	Wk2	Wk2	Wk2	Wk3	Wk3	Wk3	Wk3	Wk4	Wk4	Wk5	Wk5	Wk6	Wk6	Wk18	
Day of Visit	-20	1	2	3	4	5	8	9	10	11	12	15	16	17	18	19	22	25	29	32	36	39	126
Visit Window (days)	± 3	± 3	± 3	± 3	± 3	± 3	± 3	± 3	± 3	± 3	± 3	± 3	± 3	± 3	± 3	± 3	± 3	± 3	± 3	± 3	± 3	± 3	± 14
Screen Information & Consent	x																						
Study Information Sheet		x																					
Inclusion/Exclusion Criteria	x	x																					
Clinical Assessments																							
Demographics	x																						
Height	x																						
Weight	x																						
Clinical Interview	x																						
Pre-existing conditions	x																						
History or treatments	x																						
Concomitant treatments	x	x	x	x	x	x	x	x	x	x	x	x	x	x	x	x	x	x	x	x	x	x	
tDCS training session		x																					
tDCS intervention	x	x	x	x	x	x	x	x	x	x	x	x	x	x	x	x	x	x	x	x	x	x	
Rating Scales																							
MINI	x																						
IQ assessment		x																					
MADRS	x	x										x									x	x	
PHQ-9		x										x									x	x	
HAMA		x										x									x	x	
YMRS		x										x									x	x	
SDS		x										x									x	x	
Q-LES-Q		x										x									x	x	
tDCS Adverse Events Scale	x	x	x	x	x	x	x	x	x	x	x	x	x	x	x	x	x	x	x	x	x	x	
Acceptability questionnaire	x																			x	x		
EEG	x																			x			
Neuropsychological tasks (eg. SDMT, RAVLT,)		x																			x		

Location: Clinic (C), Home (H), Telephone (T)

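### Acceptability has no stated denominator and no rating when a participant stops early, and the baseline listing with LOCF lets a pre-course rating stand in

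*Combined protocol and SAP*

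**What the plan says.** All references are to the combined protocol and SAP.

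- **When the rating is taken.** Section 6.9: "At the final tDCS session, participants will complete the acceptability questionnaire".
- **How it is analysed.** Section 9.3.3 defines the outcome as "the percentage of participants rating the intervention as acceptable at the end of the 6 week course of tDCS", with 5 to 7 on a 7-point scale counted as acceptable. It does not say what the percentage is taken over.
- **The neighbouring outcomes.** Response in 9.3.2 is "divided by the total number of enrolled participants, expressed as a percentage". Retention in 9.3.3 is "the number of enrolled participants who do not drop out before the 6 week course of tDCS, divided by the total number of enrolled participants".
- **Baseline.** Section 6.6 includes the same questionnaire: "The baseline data consist of: MADRS, tDCS AEQ, Acceptability questionnaire, PHQ-9, HAMA, YMRS, SDS, Q-LES-Q, EEG, AVLT, SDMT (Appendix 2". The row "Acceptability questionnaire" in the schedule of events (section 11) carries three marks, one early and two late. The columns are broken in the text available to me, so the exact visits cannot be read.
- **General rules.** Section 9.7 promises an intention-to-treat analysis of all participants and a completer analysis. Section 9.8 imputes any missing data by last observation carried forward (LOCF). Neither is limited to particular outcomes.
- **People who leave.** Section 6.10 records reasons for withdrawal and says that "there will have a telephone follow up at 1 month following their withdrawal". It does not attach the acceptability question to that call or to the moment of stopping.

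**The concern.** Acceptability is a secondary objective, and section 1 says the findings will be applied to the design of a multi-site sham-controlled trial. Those who stop early are plausibly among the people least content with the sessions, and they are the ones for whom no on-treatment rating is planned.

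The missing denominator adds to this. Sections 9.3.3, 9.7 and 9.8 leave at least three calculations open: among those who rated, over all enrolled with the unrated counted as not acceptable, and over all enrolled with the last available rating carried forward. For an early stopper, the last available rating may be the baseline one. The item in 9.3.3 asks how acceptable the person found the sessions. An answer given before the course cannot report that.

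**Working it through.** **Inputs**

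- 50 enrolled, 45 completing, 10% attrition: section 9.1 (repeated in 6.1).
- Pilot discontinuation, 2 of 26: section 1.1.
- Acceptable means a rating of 5 to 7: section 9.3.3.
- 40 favourable ratings among 45 completers: my assumption, since the documents give no expected rate.
- 20% stopping: my assumption, to show a less favourable case.

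**Step 1. The plan's own figure.** 45 / (1 − 0.10) = 50, which reproduces the stated enrolment. Planned stoppers: 50 − 45 = 5.

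**Step 2. Three readings of the same data.** Let N be the number enrolled, C the number who complete and rate, k the favourable ratings among them, D = N − C the stoppers, and b the stoppers whose baseline rating was 5 to 7.

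- Among raters: k / C = 40/45 = 88.9%.
- Over all enrolled, unrated counted as not acceptable: k / N = 40/50 = 80.0%.
- Over all enrolled with baseline LOCF: (k + b) / N. With b = 5 this is 45/50 = 90.0%; with b = 0 it is 40/50 = 80.0%.

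**Step 3. Dependence on the assumed 40.** The ratio of the second reading to the first is C / N = 45/50 = 0.90, whatever k is. So 45/45 = 100% becomes 45/50 = 90%, and 36/45 = 80.0% becomes 36/50 = 72.0%.

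**Step 4. Dependence on the stopping rate.** The pilot rate is 2/26 = 7.7%, and 50 × 0.077 = 3.8, so about 4 stoppers. I keep the favourable share among raters near 89 to 90%.

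| Stoppers of 50 | Among raters | Unrated counted as not acceptable | Baseline LOCF, all stoppers favourable at baseline |
|---|---|---|---|
| 4 (about the pilot rate) | 41/46 = 89.1% | 41/50 = 82.0% | 45/50 = 90.0% |
| 5 (planned) | 40/45 = 88.9% | 40/50 = 80.0% | 45/50 = 90.0% |
| 10 (assumed) | 36/40 = 90.0% | 36/50 = 72.0% | 46/50 = 92.0% |

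**Step 5. When each reading overstates.** Suppose s of the 5 stoppers would have rated the sessions 5 to 7 on stopping. The figure for everyone enrolled is then (40 + s) / 50, between 80% and 90%. The percentage among raters (88.9%) is too high for s = 4 or fewer (44/50 = 88.0%) and slightly too low for s = 5 (90.0%). The LOCF figure is too high by (b − s) / 50, or 2 points for each person whose favourable baseline view did not survive the sessions.

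**The case against.** The strongest reply is that the plan already covers everyone. Section 9.7 includes all participants, 9.8 fills any missing value, and a completer analysis sits alongside. Read literally, that gives an all-participant figure and a completer figure. This much stands: a reader might infer from 6.9 that acceptability is asked only at the final session and that the percentage is restricted to those who got there. The documents do not support either inference. The questionnaire is also listed at baseline and marked three times in the schedule, and the denominator is unstated rather than restricted. The general rules still do not settle the matter, because the value that LOCF supplies may predate the course.

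Other points also stand, in part:

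- It would be too strong to say that people who leave are never heard. Reasons for withdrawal are recorded, a 1-month call is planned, and the adverse events questionnaire is given at each session. None of these is said to include the acceptability scale.
- Stopping tDCS is not the same as withdrawal. The compliance rule in 6.10 refers to 10 of 21 sessions, so someone who stops after that may still reach the end-of-course assessment and be rated.
- A reader might take the gap between 89% and 80% as a 9-point overstatement. That holds only if none of the 5 stoppers would have rated the sessions acceptable, and people also leave for other reasons.
- Counting the unrated as not acceptable mixes acceptability with retention, which is already reported over all enrolled. That figure therefore belongs beside the percentage among raters, labelled as a bound.
- The outcome is descriptive, with no test or threshold attached. Sample size and the primary result are unaffected.

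**Conclusion.** The concern holds in this limited form. No rating is planned when a participant stops early, the denominator is undefined, and the general LOCF rule may substitute a baseline rating. Following the plan as written can therefore overstate acceptability, whether stoppers are left out or filled in.

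At the planned 5 stoppers and an assumed 40 favourable ratings, the reported figure could be 80%, 89% or 90% depending on the reading. The 80% is a lower bound. The size of any real bias cannot be known from the documents, because it depends on how stoppers would have answered. The calculation assumes that every completer rates and no stopper does; any stopper who is rated at the end of the course narrows the range. The point is worth correcting because acceptability is a stated objective and the correction is small.

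**What to change.** - **Sections 6.9 and 6.10.** Ask the same 7-point question when a participant stops tDCS, or at the 1-month withdrawal call, subject to consent and capacity. The moment of stopping is the safer choice, since 6.10 leaves unclear whether the call follows every withdrawal.
- **Section 9.3.3.** Report ratings of 5 to 7 over all enrolled, with never-rated participants shown as a separate count and treated as not acceptable, labelled as a lower bound. Give the percentage among raters beside it, with its denominator.
- **Section 9.8.** State that a baseline acceptability rating is not carried forward. Without this, the amended 9.3.3 and the general LOCF rule would conflict.

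The cost is one added question, short wording changes in these sections, and a stated figure that may look slightly less favourable.

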6.10 Withdrawal criteria

Participants will be withdrawn from the trial if they do not comply with the intervention, namely if they are unable to have a minimum of 50% of the tDCS session (10 out of 21 sessions), or if they develop serious adverse effects from any part of the study. Recording of the reasons for withdrawal will be made. Should a participant lose capacity to consent during the study then they would be withdrawn from the study, and that their identifiable data already collected with consent would be retained for use, and that no further data collection would take place. Their GP will be informed about their withdrawal, and there will have a telephone follow up at 1 month following their withdrawal.

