2.7 Table of endpoints/outcomes

Objectives	Outcome Measures	Timepoint of evaluation of this outcome measure
Primary Objective To assess the efficacy of tDCS treatment.	Clinical response as measured by MADRS score improvement of >= 50% following the course of tDCS treatment	End of tDCS sessions (visit 21)
Secondary Objectives To assess the acceptability and safety of the intervention	Participant retention at the end of the treatment who have completed a minimum of 15 tDCS sessions Participant acceptability questionnaire scales tDCS Adverse Events Questionnaire	End of tDCS sessions (visit 21) At each session

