9.4 Subgroup analyses: N/A

9.5 Adjusted analysis: N/A

9.6 Interim analysis and criteria for the premature termination of the trial: N/A

9.7 Participant population

All participants will be included in the analysis in an intention to treat analysis and participants who have completed the study will be included in a completer analysis.

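### Section 6.10 withdraws low attenders and those with serious adverse effects from the trial without providing for their visit-21 MADRS, although the primary result counts everyone enrolled

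*Combined protocol and SAP*

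**What the plan says.** Section 6.10 (Withdrawal criteria) sets a mandatory rule: "Participants will be withdrawn from the trial if they do not comply with the intervention". It names two triggers. The first is attendance, "namely if they are unable to have a minimum of 50% of the tDCS session (10 out of 21 sessions"; the second is "or if they develop serious adverse effects from any part of the study". It then deals with loss of capacity, and only in that sentence says that "no further data collection would take place". For contact after withdrawal it says that the GP is informed and that "there will have a telephone follow up at 1 month following their withdrawal". No assessment is named for that call.

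Table 2.7 ties the primary MADRS response to "End of tDCS sessions (visit 21". The schedule of events (section 11) puts visit 21 on Day 39 (±3) and the follow-up on Day 126, Week 18 (±14). It shows no early-termination visit.

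On the analysis side, 9.3.2 defines the primary result as responders "divided by the total number of enrolled participants, expressed as a percentage". Section 9.7 says "All participants will be included in the analysis in an intention to treat analysis" and adds a completer analysis. Section 9.8 fills any missing value by last observation carried forward (LOCF).

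**The concern.** Stopping a treatment and leaving a trial are different events, and 6.10 merges them. A participant who has had too few sessions, or a serious adverse effect, may still be willing to be rated on Day 39. A site that follows 6.10 has no instruction to rate that person, and sites may differ in what they do.

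The analysis sections still keep that person in the denominator. Missing primary outcomes would therefore arise for reasons tied to adherence and harm, so they are unlikely to be missing at random, and the intention-to-treat response rate would depend on LOCF for exactly these people. The completer analysis does not help, because it leaves them out.

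The other end-of-treatment scales (YMRS, PHQ-9, HAMA, SDS, Q-LES-Q) could go missing for the same people. YMRS matters most. Section 1.1 puts treatment-emergent mania or hypomania at around 4% with active tDCS, which is 0.04 × 50 = 2 participants here. Section 6.10 does not define serious adverse effects, so it is uncertain whether such a case would trigger withdrawal.

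Section 1 says that the findings will feed the design of a randomised sham-controlled trial, so any error in the response rate carries forward.

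**Working it through.** **1. The plan's own figure.** Section 9.1 gives 45 completers, 10% attrition and 50 enrolled. 45 / (1 − 0.10) = 50, which reproduces. Planned non-completers: 50 − 45 = 5.

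**2. Weight of a missing rating.** The denominator in 9.3.2 is all enrolled, so one participant is 1/50 = 2 percentage points. With r observed responders and m participants without a visit-21 MADRS, the response rate lies between r/50 and (r + m)/50, a width of m/50.

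| m | Width |
|---|---|
| 2 | 4 points |
| 5 (all planned attrition) | 10 points |

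Illustrations for m = 5, with assumed observed responders among the other 45:

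| Observed | Lower bound | Upper bound |
|---|---|---|
| 14/45 | 14/50 = 28% | 19/50 = 38% |
| 22/45 | 22/50 = 44% | 27/50 = 54% |
| 31/45 | 31/50 = 62% | 36/50 = 72% |

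For comparison, the pilot in 1.1 had 2 discontinuations among 26. Scaled to this trial, 2/26 × 50 = 3.8, or about 4 people and 8 points. The documents do not say how many non-completers, in the pilot or here, would leave by the 6.10 route.

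**3. When the attendance trigger bites.** With a minimum of 10 of 21, the shortfall is certain once 12 sessions are missed (21 − 12 = 9). A participant who has attended k sessions reaches that point at session 12 + k. The earliest is session 12 (k = 0), Day 16 in the schedule; k = 5 gives session 17, Day 25. The two forms of the threshold in 6.10 do not agree (50% of 21 is 10.5; 10/21 = 47.6%) and must be reconciled. Read as 11 sessions, the shortfall is certain at the 11th missed session, at the earliest Day 15.

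**4. What LOCF would carry.** The schedule marks a mid-treatment MADRS at about visit 10 or 11 (the table is broken in the text available), near or before those dates. The carried value is therefore the mid-treatment score or, if that was not taken, the baseline score.
- Baseline carried: change is zero, so the participant counts as a non-responder. If the true Day 39 state is response, the rate is 2 points too low.
- Mid-treatment non-response carried: same direction of error if the participant later improved.
- Mid-treatment response carried: if the participant has relapsed by Day 39, the rate is 2 points too high.

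The errors can go either way, and nothing in the documents fixes their balance.

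**The case against.** A reader might infer that the visit-21 MADRS is never taken for these participants. The documents do not say so. The bar on further data collection is written only for loss of capacity, and that contrast can be read as leaving collection open for the other two triggers. Section 8.9 records adverse events for 3 months after the last tDCS, and the schedule appears to allow telephone contact at follow-up, where MADRS is marked. This stands: what can be shown is that no rating is provided for, not that one is forbidden.

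A reader might also picture someone who attends nine sessions and is removed before Day 39. The rule does not produce that case by itself. With nine attended, the shortfall is certain only at session 9 + 12 = 21, which is visit 21. An earlier exit needs a lower attendance, an earlier judgement that the participant is unable to continue, or a voluntary stop that 6.10 does not cause. Likewise, a serious adverse effect after visit 21 removes no visit-21 score. These points narrow the group affected.

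The size is also open to challenge. The 10% attrition covers all non-completion. Section 1.1 cites no reports of serious adverse effects in over 33,200 sessions, so that trigger may be rare. The full band needs all of the missing participants to respond at one end and none at the other. Sampling error is larger: at 50% response with n = 50, 1.96 × √(0.25/50) = 0.139, an interval about 28 points wide, in an open-label proof-of-concept study. All of this is fair. But sampling error is reported with an interval, whereas this error would not show in one, and it can be reduced at little cost.

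Finally, LOCF makes the reported rate determinate. That is true, but it settles which number is printed, not whether the number is right. Whether LOCF is a good rule is a separate matter; the point here is that the rating it replaces could often be obtained.

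**Conclusion.** The point holds in a limited form. Section 6.10 takes two groups out of the trial, no section provides for their visit-21 MADRS, and 9.3.2 and 9.7 still count them, so their primary outcome would rest on a carried-forward mid-treatment or baseline score. The size is 2 percentage points per participant: 4 points for two and at most 10 for five. The 10-point figure is an upper case that assumes all planned attrition takes this route and that none of the five is rated.

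Two stronger conclusions are not supported. The protocol does not prohibit the rating. Nor can it be said that rating these participants would lower the response rate: they are already in the denominator, and where LOCF scores them as non-responders a rating can only leave the rate unchanged or raise it. It can fall only where a mid-treatment response was carried forward.

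This does not invalidate the trial. It is an avoidable source of bias in the primary result that an inexpensive change reduces.

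**What to change.** 1. In 6.10, separate stopping tDCS from withdrawing from the trial. Leave the criteria for stopping as they are, apart from reconciling the two forms of the attendance threshold; no view is taken here on that rule.
2. State that participants who stop for low attendance or serious adverse effects are still asked for the scheduled MADRS, YMRS and self-report scales at Day 39 (±3) and at the Week 18 follow-up, unless consent is withdrawn or capacity is lost.
3. In table 2.7, anchor the primary assessment to Day 39 (±3), whatever the number of sessions attended.
4. For consistency, say how a participant who has stopped tDCS but is still rated counts towards retention (2.5, 9.3.3) and the completer analysis (9.7), since both depend on who is taken to have dropped out or completed.

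The cost is one amendment and, for perhaps 2 to 5 participants, ratings that the schedule already contains. Some will decline, so a few values will still be missing. The reported response rate could move either way.

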2.5 Secondary endpoints/outcomes

- 1) Participant retention at the end of the treatment who have completed a minimum of 15 tDCS sessions
- 2) Participant acceptability questionnaire scales
- 3) tDCS Adverse Events Questionnaire at each session (Brunoni et al., 2011)

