7.4 Drug storage and supply (if applicable): N/A

7.5 Preparation and labelling of Investigational Medicinal Product (if applicable): N/A

7.6 Dosage schedules:

The Flow Neuroscience tDCS headset will be delivered to the participant's home. The device is designed and approved (CE) to be used at home without supervision.

6-week course of active tDCS treatment, consisting of 5 sessions per week for the first 3 weeks followed by 2 sessions per week for 3 weeks, for a total of 21 tDCS sessions. Duration of each session is 30 minutes. We will use the Flow Neuroscience tDCS device (Figure 1) with a bifrontal montage: anode at left dorsolateral prefrontal cortex (DLPFC) and cathode at right DLPFC (EEG positions F3 and F4, respectively). Stimulation is 2 mA, and electrode area is 35 cm². During each session, participant will be seated comfortably with their eyes open, and research assistant will provide a discreet presence without interacting with the participant by video call.

tDCS parameters are based on meta-analyses (Meron et al., 2015; Dondé et al., 2017; Mutz et al., 2018) indicating that effects are greatest at 2 mA current of 30-minute stimulus. The tDCS equipment records the duration of each session, and there is an automatic shut-off to prevent unsafe use.

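### Section 6.10 equates a 50% session minimum with 10 of 21 sessions, but 10 of 21 is 47.6%; a 50% minimum needs 11

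*Combined protocol and SAP*

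**What the plan says.** Section 6.10 (Withdrawal criteria) removes a participant from the trial for non-compliance if they are "unable to have a minimum of 50% of the tDCS session (10 out of 21 sessions"). The same section requires the reason for withdrawal to be recorded. It goes on to describe informing the GP and a telephone follow-up one month after withdrawal.

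Section 7.6 (Dosage schedules) fixes the length of the course: "5 sessions per week for the first 3 weeks followed by 2 sessions per week for 3 weeks, for a total of 21 tDCS sessions". This regimen also appears in the Trial Summary. Section 2.7 times the primary outcome at visit 21, and the Schedule of Events in section 11 lists 21 treatment days, from day 1 to day 39.

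A different session threshold appears in section 2.5, as the first secondary endpoint: "Participant retention at the end of the treatment who have completed a minimum of 15 tDCS sessions". It defines an endpoint and does not say when a participant is to be withdrawn.

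**The concern.** The bracket in section 6.10 is presented as the 50% minimum expressed as a count, but 10 sessions out of 21 is less than half. Nothing in the documents says which figure takes precedence or how to round.

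Staff have to apply this rule to individual participants. Under section 7.11 the device records each session's duration and a research assistant is present at each session, so the number of sessions will be known; only the cut-off is unclear. At exactly 10 sessions the percentage says withdraw and the count, as it naturally reads, says keep. Two sites could handle the same participant differently, and both could cite section 6.10.

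**Working it through.** **Inputs**

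- Minimum share of sessions: 50% (section 6.10).
- Count given for that minimum: "10 out of 21 sessions" (section 6.10).
- Regimen: 5 sessions a week for 3 weeks, then 2 a week for 3 weeks (section 7.6 and Trial Summary).
- Planned enrolment 50, with 10% attrition (section 9.1).
- Discontinuation in the unipolar pilot: 2 of 26 (section 1.1).

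**Denominator.** 5 × 3 + 2 × 3 = 15 + 6 = 21 sessions. This reproduces the plan's total.

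**Threshold.** 0.50 × 21 = 10.5. A minimum has to be reached, so the smallest whole count that satisfies it is 10.5 rounded up, which is 11.

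| Sessions attended | Share of 21 | Meets 50%? |
|---|---|---|
| 10 | 10/21 = 47.6% | No |
| 11 | 11/21 = 52.4% | Yes |

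**Can the plan's 10 be reproduced?** Only by rounding 10.5 down, which gives a count below the stated minimum, or by dividing by 20 (10/20 = 50.0%), which contradicts the 21 printed in the same bracket.

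**In missed sessions.**

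- At least 11 required: 21 − 11 = 10 misses are tolerated, and the 11th triggers withdrawal.
- At least 10 required: 21 − 10 = 11 misses are tolerated, and the 12th triggers withdrawal.

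The two readings differ only for a participant with exactly 10 sessions attended and 11 missed.

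**How many participants might that be?** The documents give no distribution of sessions among non-completers. Assume, for illustration only, an even spread over the 21 values from 0 to 20.

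- At 10% attrition: 50 × 0.10 = 5 non-completers; 5/21 = 0.24 expected at exactly 10 sessions.
- At the pilot rate: 50 × 2/26 = 3.85; 3.85/21 = 0.18 expected.

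Both figures include people who stop of their own accord, for whom the rule changes little.

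**Effect on the analyses.**

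- Primary outcome (section 9.3.2): the denominator is all enrolled participants, so it does not change.
- 15-session retention endpoint (sections 2.5 and 2.7): 15/21 = 71.4%; 10 sessions fails it under either reading.
- Sample size (section 9.1): does not use this rule.
- Retention as worded in section 9.3.3, the completer set (section 9.7) and last observation carried forward (section 9.8): these would be touched only if withdrawal for non-compliance counts as drop-out or ends MADRS assessment. The documents do not state either, so no effect is claimed.

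**The case against.** The strongest reply is that this is rounding. No whole number is exactly half of 21, and a bracketed count after a percentage is ordinarily its working definition, so staff would simply apply 10. It is true that the count is the easier figure to use against a session log. But a stated minimum cannot be met by rounding down, and the text neither calls the percentage approximate nor says that the count governs.

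A second reply is that the sentence describes who is withdrawn, so the bracket may mark the failing count: 10 or fewer means withdrawal. That would agree exactly with a 50% minimum. The reading is possible, but the word order is against it, because the bracket follows the minimum and reads as that minimum expressed in sessions. If it was intended, requiring at least 11 of 21 sessions states the same rule plainly.

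Third, the participant numbers are soft. This stands. The even spread has no basis in the documents. Someone who has already left is hardly affected by a non-compliance rule, and if the 11th miss falls late there is little treatment left to stop. The figures show only that the expected number is well below one.

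Finally, the choice between 10 and 11 belongs to the sponsor, and the documents do not settle which was meant. This also stands. The case for 11 as the default is only that it preserves the percentage the protocol states.

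**Conclusion.** The point holds. As written, section 6.10 gives a count (47.6%) that does not meet its own 50% minimum; the smallest count that does is 11 of 21 (52.4%). This follows from figures in the protocol alone and needs no outside source or modelling assumption.

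The impact is minor. The discrepancy is one session, confined to a participant still taking part with exactly 10 attended. On the assumed even spread that is about 0.18 to 0.24 of a participant among the 50 enrolled, so most likely nobody. No effect on the primary result, the 15-session endpoint or the sample size follows from it. It is worth correcting because it is a decision threshold for individual participants and should give a single answer.

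**What to change.** In section 6.10, replace the bracketed count with *at least 11 of 21 sessions*, which keeps the stated 50% minimum. If 10 is the intended cut-off, write *at least 10 of 21 sessions, about 48%* and remove the 50%. Either way, the section should express the rule once, as a count of sessions attended.

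The cost is one line of protocol wording. No analysis, sample size or schedule changes.
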